3.0 INTRODUCTION

In Mexico, the prevalence of overweight and obesity has increased among children at an alarming rate over the past three decades, partially because of the increased intake of sugary beverages that have high caloric content and low nutritional status. The major types of beverages that provide the most energy intake are soft drinks, beverages made from fruit juice (with or without added sugar), flavored water, and natural juices added with sugar and whole milk.

Energy consumption from these beverages doubled for all age groups from 1999 to 2012; when added to the energy obtained from food in the diet, these drinks contributed to an excessive intake of energy linked to the development of obesity.

The Mexican government identified the promotion of water consumption as a major strategy to reduce the energy density of the diet and thus at least partially prevent the problems of overweight, obesity, and other diseases associated with the excessive intake of sugary beverages. Therefore, the National Agreement for Nutritional Health (ANSA, in Spanish) considers increasing the intake of water and discouraging the consumption of sugary beverages as priorities for this population.

Given the evidence that school provides an optimal environment to conduct nutritional promotion programs that encourage the practice of healthy lifestyles that include the promotion of water consumption, a need arose to create such an educational strategy. Ogali (Nutrition Consulting Company: www.ogali.com) designed the educational strategy “I Prefer Plain Water”, and it demonstrated short-term effectiveness by increasing the consumption of water and reducing the consumption of sugary beverages and soft drinks. However, it is unknown whether these observed changes are sustainable throughout early elementary education, a period that education specialists have established as essential to forming healthy habits for life.

Evaluating the long-term (1-year) effectiveness of this program is necessary because the knowledge gained will help determine the number of interventions that children should receive to maintain a healthy water-consumption pattern to establish public health policies that allow children to maintain a healthy lifestyle that affects their quality of life.

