7.1 Primary Objective

This study seeks to compare the percentage of water consumed among early elementary school children receiving one, two, or three interventions of the educational strategy "I Prefer Plain Water" at a 1-year follow-up evaluation.

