8.0 HYPOTHESES

The percentage of water consumed will be greater in the group of children who will receive all three interventions.

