15.0 STATISTICAL ANALYSIS

The analysis will be performed using the IBM SPSS version 22.0, and non-parametric statistics will be used.

Baseline measurement of beverage consumption (Time 1). The basal consumption of the different beverage categories will be summarized using medians, minimums, and maximums. We will apply the Kruskal-Wallis test (K of independent samples) to compare the differences in baseline beverage consumption among the three groups.

Baseline measurement and at the end of the interventions (Times 1 and 3). The percentage of water consumed at baseline will be compared with that 1 year after finishing the intervention for each group using the Wilcoxon test.

Comparison among the three groups. The percentage of water consumed will be compared among the three groups 1 year after the intervention is completed using Friedman's test of related samples.

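### The only between-group test of the follow-up outcome is a single three-group test, with no Group III contrast and no interval, so it cannot test the stated hypothesis or show the gain from a second or third intervention

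*Combined protocol and SAP*

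**What the plan says.** Three places set the question.

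- Section 3.0 (Introduction) expects the results to "help determine the number of interventions that children should receive to maintain a healthy water-consumption pattern".
- Section 7.1 (Primary Objective) is to "compare the percentage of water consumed among early elementary school children receiving one, two, or three interventions".
- Section 8.0 (Hypotheses) is directional and names one group: "The percentage of water consumed will be greater in the group of children who will receive all three interventions".

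Section 15.0 (Statistical Analysis) answers with three analyses.

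- A baseline Kruskal-Wallis test to "compare the differences in baseline beverage consumption among the three groups".
- Within-group tests: "The percentage of water consumed at baseline will be compared with that 1 year after finishing the intervention for each group using the Wilcoxon test".
- One follow-up comparison, by Friedman's test: "The percentage of water consumed will be compared among the three groups 1 year after the intervention is completed".

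Neither Section 15.0 nor any other section gives a pairwise contrast, a trend test, a multiplicity rule, a between-group estimate with an interval, or a statement of which result would support the hypothesis. The statistical paragraph of the Summary (1.0) lists only the baseline and within-group tests.

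**The concern.** The question has three ordered levels and a directional claim about the top one. A three-group test can conclude only that the groups are not all alike. It rejects when Group III is best, when Group II is best, and when II and III are equal and both exceed I. The hypothesis is true only in the first case.

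Nor does a single p-value say how much a second or third round of sessions adds, which is what Section 3.0 wants to know. If the contrasts are left to be chosen after the data are seen, the pairs, any correction and the reading are all open. If the test is not significant, no interval shows what gain has been excluded.

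This is separate from the choice of Friedman's test. That test needs matched measurements, and the three groups are different children in different schools. A valid independent-groups omnibus test would still leave the hypothesis untested.

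**Working it through.** **Inputs.** Section 13.0 gives a difference of 80.74 mL, SD 399 mL, α 0.05, β 0.1, a 28% loss margin, and groups of 81, 81 and 167 first graders (Group III is two schools, 64 + 103). After 28% loss: 81 × 0.72 ≈ 58 and 167 × 0.72 ≈ 120. The documents give no SD or target difference for the percentage of water, so the mL figures stand in for it, and 399 mL is assumed to apply within each group.

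**The plan's own figure.** (1.96 + 1.28)² × 399² / 80.74² = 256.36, rounded up to 257. It reproduces. It is a one-sample or paired formula giving one total, so no between-group contrast is implied there either.

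**Planning effect in SD units.** 80.74 / 399 = 0.20.

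**What an omnibus rejection says.** Kruskal-Wallis was simulated as the valid replacement, with normal data, independent children and 4,000 runs per pattern, at 58/58/120:

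| True pattern | Section 8.0 hypothesis | Rejects at 0.20 SD | Rejects at 0.5 SD |
|---|---|---|---|
| Only III better | true | 24% | 92% |
| Only II better | false | 20% | 81% |
| II = III, both above I | false | 19% | 82% |

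At the enrolled sizes (81/81/167) and 0.20 SD, it rejects in about 34% of trials when only III is better. When II = III > I it rejects in about 26%, and in about 13% it rejects with Group III's median the highest. At 0.5 SD with II = III > I these last two figures are about 93% and 46%. The 0.5 SD shift is illustrative and does not come from the documents.

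**What naming the contrasts does.** Take the rule that III vs I and III vs II must both be significant in favour of III.

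- II = III > I by 0.5 SD, independent children: false claim in about 3%.
- Same pattern with an assumed school ICC of 0.02 to 0.05 (the documents give none): about 9% to 16%. Repeat runs vary by a point or two.
- Only III better by 0.20 SD, independent children: success in about 14%, or 8% after loss.
- Graded pattern (0, 0.25, 0.5 SD), independent children, 81/81/167: success in about 44%, against 91% for the omnibus test.

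**Precision of one contrast, clustering ignored.** For III vs I, SE = 399 × √(1/81 + 1/167) = 54.0 mL, so the 95% CI is about ± 1.96 × 54.0 = 106 mL. After loss, SE = 54.0 / √0.72 = 63.7 mL and the half-width is about 125 mL. Both exceed 80.74 mL. Power is Φ(80.74/54.0 − 1.96) = 32%, or 25% after loss. For II vs I it is 25%, or 19% after loss. A non-significant contrast is therefore the likely outcome even if the planning difference is real.

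**The case against.** **The objective is only to compare, and the Introduction promises only help.** This is fair as far as it goes, and a valid omnibus test partly serves a bare comparison. It does not serve Section 8.0, which makes a directional claim about Group III.

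**The remaining tests fill the gap.** They do not. The Kruskal-Wallis test is between groups, but at baseline. The Wilcoxon tests are within group. With 81, 81 and 167 children, the same change is more likely to reach significance in Group III, so comparing their p-values would favour the hypothesised group.

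**The real obstacle is the design.** This stands. Section 12.4 assigns schools by enrolment and teacher interest. Section 13.0 puts one school in Group I, one in Group II and two in Group III. Section 12.5 places the one-year record at the end of 2nd, 3rd and 4th grade respectively. A reader might infer that adding contrasts would let the trial choose a number of interventions. It would not: the number is confounded with school, grade and calendar year whatever test is used.

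**The effect is chosen to impress.** This stands against taking 93% and 46% as the size of the problem. At the protocol's 0.20 SD those figures are about 26% and 13%.

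**The readings feared are conjecture.** This also stands. A reader might infer that a significant result will be reported as support for three interventions, or a non-significant one as showing that one is enough. The documents state neither. They leave the reading undefined.

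**Conclusion.** The point holds. Followed as written, the plan cannot test its own directional hypothesis and gives no estimate of the gain from a second or third intervention. At the 0.20 SD implied by Section 13.0, an omnibus rejection is only somewhat more likely when Group III alone is better (about 34%) than when II and III are equal and above I (about 26%). These figures assume normal, independent child-level data and borrow the mL effect size for an outcome measured in percent.

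Two stronger readings are not supported. First, the missing contrasts are not the only reason why the trial cannot settle the number of interventions, because the allocation and the follow-up schedule also prevent it. Second, requiring both contrasts at 0.05 does not guarantee error control here. No further correction is needed for independent children, but with school clustering the false-claim rate can exceed 5%.

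**What to change.** In Section 15.0:

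1. Use an independent-groups analysis for the follow-up comparison.
2. Prespecify III vs I and III vs II as the test of the Section 8.0 hypothesis, supported only if both favour Group III. Make II vs I secondary.
3. Report each difference in percentage of water with a 95% CI.
4. State that a non-significant contrast is not evidence that fewer interventions suffice, and that any such reading must rest on the interval.
5. State that child-level p-values and intervals ignore school clustering. State also that, with one or two non-randomised schools per group and follow-up at different grades, the contrasts describe differences between these groups and cannot by themselves be attributed to the number of interventions.

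The cost is a few lines of text and three contrasts on data already being collected. The downside is a stricter test: about 14% success (8% after 28% loss) if Group III alone is better by 0.20 SD. The intervals, not the p-values, should therefore carry the interpretation.

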After water, dairy drinks were consumed most often, with a similar median for both groups throughout the trial (i.e., no significant differences). The consumption of hot drinks, soft drinks, and functional beverages was low and did not significantly change throughout the trial.

Figure 1. Change in beverage consumption, Intervention Group (IG) vs Control Group (CG)

* Friedman related samples

The “I Prefer Plain Water” educational strategy effectively increased the consumption of water and reduced the consumption of sugary beverages and soft drinks when evaluated over the short term (4 months after its implementation); however, its long-term effectiveness (1 year later) has not been established.

According to the transtheoric model that uses the stages of change to integrate the processes and principles of change through the main theories of intervention, the maintenance stage in which the change in behavior persists occurs when the behavior is maintained for 6 months or more (17). Based on this idea, the effectiveness of this educational strategy will be evaluated 1 year after the intervention.

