9.0 STUDY DESIGN

Experimental, analytical, longitudinal, and prospective designs will be employed. The assignment will be conducted by each school.

Community Intervention Test

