12.4 Intervention

At all participating schools, the principal investigator will conduct an approximately 1-hour briefing for parents to 1) explain the study's operational generalities and answer all questions and 2) provide instructions for completing the beverage consumption survey. Subsequently, the 3-day baseline record of beverage consumption will be collected.

At the beginning of the school year, first grade teachers will be trained by a nutritionist (one per school) to dispense the educational sessions (Appendix VI, VII, VIII), and the manual and materials for both teachers and students will be delivered.

The students will receive four educational sessions of approximately 1 hour. These sessions will be given every 2 weeks, and some will be supervised by a nutritionist.

The four schools will be assigned to one of the following three groups based on school enrollment and the interest of the teachers in participating:

Students in Group I will receive the education strategy only during the first grade; students in Group II will receive the educational strategy during first and second grades; and students in Group III will receive the educational strategy during first, second, and third grades.

	1st grade	2nd grade	3rd grade
Group I	X		
Group II	X	X	
Group III	X	X	X

With the delivery of the first educational session, free access to water will be initiated through Welltek water dispensers, model WT-POU-300 A (approved and certified by Cofepris and the National Institute of Physical Educational Infrastructure; INIFED), installed inside the classrooms. Children will also receive a reusable 600-mL bottle (twice) so that they may consume water throughout the day. The availability of water will be guaranteed during four school cycles.

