12.5 Evaluation Process

In September 2017, the medical examination of the students and the process of inclusion will be performed; instructions will be sent to parents, and teacher training will be conducted. During October 2017, the baseline record regarding the consumption of beverages will be collected (Time 1). The educational sessions will be given from November 2017 to January 2018. A second record (Time 2) will be obtained at the end of the interventions in each group (end of June), and a third record (Time 3) will be obtained from each group 1 year after completing the interventions (end of June).

Baseline		End of 1st grade	End of 2nd grade	End of 3rd grade	End of 4th grade
Group I	X	X	X		
Group II	X	X		X	
Group III	X	X			X

 Evaluation 1 year after completing the number of interventions associated with each group

In addition to measurements at baseline and at each evaluation time, body weight will be measured, and lean mass, fat free mass, fat percentage, total body water, and BMI will be analyzed using a body composition analyzer via electrical bioimpedance (TANITA TBF-310 GS). Height will be measured using a portable stadiometer (dry mark, model 213, Hambur Germany). Participants will be measured in light clothing (T-shirt and sport shorts) and without shoes. A nutritionist will be calibrated to perform the measurements. BMI will be classified using the WHO values standardized by age and gender.

The following table summarizes the procedures to be performed throughout the trial.

Procedure	Sep 2017	Jun 2018	Sep 2018	Jun 2019	Sep 2019	Jun 2020	Sep 2020	Jun 2021
School medical examination	X							
Weight, size, and body composition measurements	X	X		X		X		X
Instructions for completing the daily beverage record	X	X		X		X		X
Teacher training	X		X		X			
Daily beverage record	X	X		X		X		X
Group I intervention	X							
Group II Intervention	X							
Group III Intervention	X							

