13.0 SAMPLE SIZE

Considering the results of the previous study where a mean difference of 80.74 mL was found with regard to water consumption with an SD of 399 mL as well as considering an α of 0.05 and a β of 0.1, we used the following formula to calculate a significant difference in means

$$n = [(Z_{1-\alpha} + Z_{1-\beta})^2 * s^2] / d^2$$
$$[(1.96 + 1.28)^2 * 399^2] / 80.74^2 = 256.36$$

N = 257 children

The sample should include 329 first graders (allowing for a 28% loss margin) who will attend the 2017-2018 school year. This sample represents all of the four intervention schools that participated in the previous study.

2016-2017 school enrollment of the intervention schools participating in the previous study

School	Health Center	First grade	Total	Second grade	Total	Third grade	Total	Total school enrollment
Ramón Durand	Ajusco	32 32	64	31 32	63	26 27	53	341
Xitle	Ajusco	27 29 25	81	28 27 29	84	31 30 29	90	529
Guillén de Lampart	Santa Úrsula	28 26 27	81	31 32 30	93	27 27	54	475
Tlamatini	Santa Úrsula	34 35 34	103	36 37 36	101	33 33 33	99	600
			329		278		243	1,604

	Group I	Xitle	81
	Group II	Guillén de Lampart	81
	Group III	Ramón Durand Tlamatini	167

Based on the school enrollment of the current school year (2016-2017), schools with the same number of first graders will be assigned to Groups I and II. For Group III, the schools with the highest and lowest enrollments will be added.

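### Friedman's related-samples test is planned for the primary comparison of three separate groups of children, so that comparison cannot be run as written

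*Combined protocol and SAP*

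**What the plan says.** The primary objective (Section 7.1) is to "compare the percentage of water consumed among early elementary school children receiving one, two, or three interventions" at the 1-year evaluation. Section 8.0 predicts the highest percentage in the three-intervention group.

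Section 15.0 gives the only test for this question: the percentage of water will be "compared among the three groups 1 year after the intervention is completed using Friedman's test of related samples". For the same three groups at baseline, the same section says "We will apply the Kruskal-Wallis test (K of independent samples"). The Summary names only the baseline Kruskal-Wallis test and the within-group Wilcoxon tests.

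On the design, Section 9.0 states "The assignment will be conducted by each school". Section 12.4 has the four schools "assigned to one of the following three groups based on school enrollment and the interest of the teachers in participating". Section 13.0 adds that "schools with the same number of first graders will be assigned to Groups I and II" (81 children each), while Group III combines the largest and smallest schools (103 + 64 = 167). Section 12.5 says "a third record (Time 3) will be obtained from each group 1 year after completing the interventions", which its table places at the end of 2nd, 3rd and 4th grade for Groups I, II and III.

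**The concern.** Friedman's test needs one value under every condition in each block, normally the same person measured repeatedly or a matched set. Groups I, II and III are different children in different schools, measured in different years, and no matching is described. Section 15.0 also contradicts itself by treating these groups as independent at baseline and as related at follow-up.

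The primary objective and the hypothesis both depend on this comparison. The baseline Kruskal-Wallis test and the within-group Wilcoxon tests do not compare one, two and three interventions at follow-up. Left as it is, the primary test would be chosen after the data are seen, or the groups would be set side by side in arbitrary rows and the answer would depend on how the file was sorted.

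**Working it through.** **1. The plan's own figures (Section 13.0).** (1.96 + 1.28)² × 399² / 80.74² = 256.36, so 257; 257 × 1.28 = 328.96, so 329; and 81 + 81 + 167 = 329. All reproduce. The formula is for one sample or paired data, in mL, so it does not size the between-group comparison of percentages. It is used here only for scale: 80.74 / 399 = 0.20 SD.

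**2. Count the blocks.**

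| | Group I | Group II | Group III |
|---|---|---|---|
| Schools | 1 | 1 | 2 |
| First graders | 81 | 81 | 64 + 103 = 167 |
| After 28% loss (× 0.72) | 58 | 58 | 46 + 74 = 120 |
| Time 3 | end of 2nd grade | end of 3rd grade | end of 4th grade |
| Time 3 values per child | 1 | 1 | 1 |

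With k = 3 conditions and n complete blocks, the statistic is 12 / [n k (k + 1)] × ΣRⱼ² − 3n(k + 1), where Rⱼ is the rank sum of group j. No child has a value in more than one group, so n = 0 and the statistic is undefined. Running Friedman's test on columns of 81/81/167 or 58/58/120 stops with an error; Kruskal-Wallis runs on both.

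**3. What forcing it would cost.** Lining up unrelated children keeps 58 rows and drops 120 − 58 = 62 of 120 Group III children (52%). At full enrolment it drops 167 − 81 = 86 of 167 (51%). Simulation used 10,000 trials per scenario, normal data, independent children, a random 58 from Group III for Friedman, and all 58/58/120 for Kruskal-Wallis. The shifts are assumptions, except that the 0.2 SD top shift equals 80.74/399. That ratio is in mL; the documents give none for the percentage.

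| Shift I/II/III (SD) | Friedman, forced | Kruskal-Wallis |
|---|---|---|
| 0/0/0 | 4.4% | 4.7% |
| 0/0.1/0.2 | 11% | 18% |
| 0/0.25/0.5 | 51% | 79% |

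Type I error stays near 5% when children are independent; the loss is in power. Kruskal-Wallis on 58/58/58 gives about 15% and 65%, so roughly half of each gap comes from discarded children and half from the test.

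**4. Row order.** Row order also decides which Group III children are kept. With 200 data sets and 300 orders each, the median 5th to 95th percentile of the Friedman p-value ran from 0.07 to 0.89 at the small shifts and from 0.003 to 0.41 at the larger ones. Repeat runs put that last figure between 0.30 and 0.43, so treat these as approximate.

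**5. Limit of the replacement.** With no intervention effect and an assumed school intraclass correlation (ICC; the documents give none), rejection at a nominal 5% was:

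| ICC | Kruskal-Wallis, 58/58/120 | Friedman, forced | Kruskal-Wallis, 81/81/167 |
|---|---|---|---|
| 0.01 | 14% | 10% | 19% |
| 0.02 | 24% | 16% | 30% |
| 0.05 | 46% | 33% | 57% |

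**The case against.** The strongest reply is that this is a slip of the pen. The Figure 1 footnote in Section 4.5.2 reads "Friedman related samples", for repeated records in the previous study, and the name may have been carried over. That is plausible, but it is inference. The sentence in Section 15.0 compares the groups at a single time, and within-group change already has its own paragraph and test, so it cannot be read as a comparison across times.

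A second reply is that nobody plans to pair unrelated children, so the power and row-order figures describe a hypothetical analysis. That is fair. The direct consequence is simply that no executable test exists; the figures show only what a workaround would cost. The group sizes are also open to argument: 58/58/120 takes 28% off enrolment, whereas the plan's required 257 would be about 63/63/130. At those sizes power is 13% against 19% and 56% against 82%, which changes nothing of substance.

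Third, Kruskal-Wallis is not valid either once children within a school are correlated, and it then rejects a true null more often than a forced Friedman test would. This stands. Clustering and one school per group are separate design limits that the change of test does not cure, and they do not justify keeping a test that cannot be computed.

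**Conclusion.** The concern holds and must be fixed. The only between-group test of the primary outcome at follow-up requires related samples, and the design supplies none: no complete blocks, unequal groups of 81/81/167, one Time 3 value per child and no matching. This follows from the documents alone and rests on no assumption.

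The size of the loss under a forced analysis rests on normal data, independent children and the assumed shifts. The ICC results rest on assumed correlations. They show that a child-level p-value from the replacement test would still need qualification.

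**What to change.** In Section 15.0, replace Friedman's test with an independent-groups comparison of the Time 3 percentage of water.

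- At minimum, use Kruskal-Wallis across the three groups, with pre-specified contrasts III vs I and III vs II to match Section 8.0. State whether both contrasts must be met for the hypothesis to be supported. An ordered-trend test would be a reasonable alternative to the contrasts.
- State that child-level p-values do not account for assignment by school, that with one school each in Groups I and II the school and intervention effects cannot be separated, and that the between-group conclusion is qualified accordingly.
- Optionally, use rank ANCOVA with the baseline percentage already collected. The gain depends on a correlation the documents do not give.

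The cost is wording in Section 15.0, with no new data. The one-school-per-group limit remains and has to be reported as a limitation.
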